9.8.3 Validation of Endpoints

The endpoints (diagnostic accuracy, sensitivity, specificity, PPV, and NPV) are well accepted for assessing diagnostic test performance. The endpoints of inter-reader agreement and intra-reader reproducibility will not be possible because each reader will interpret only the images collected at his/her institution, and it is assumed that each reader will interpret each image only once.

9.8.4 Storage of Records including Archiving of Statistical Programming

All study documentation will be archived in accordance with ICH E6- GCP and the Sponsor/CRO's quality standards and SOPs.

The Sponsor will ensure that all study information is handled and stored to allow for accurate reporting, interpretation and verification of that information and shall ensure that the confidentiality of the records of the study subjects remains protected.

9.8.5 Certification and Qualifications of Supporting Laboratory or Research Groups

Not applicable to this study.

9.9 Limitations of the Research Methods

The main limitations of this study are:

- 1. Not all countries and sites can be represented because of restrictions due to approval and manufacturing locations.
- 2. Readers who participate may not be fully representative of the population of readers in clinical practice (e.g., untrained readers may be unwilling to participate, and there may not be a balanced split among clinical readers for subgroups such as training type, specialty, etc. since we are not controlling these factors).

The potential for bias from the first limitation cannot be assessed in this study. The potential for bias from the second limitation will be assessed by reporting demographic data (see Table 5) for readers who are randomly chosen to participate as well as the complete pool of potential readers who agreed to participate in addition to readers who decided not to participate, where data are available.

9.10 Other Aspects

Before starting this study, the protocol (authorised by the Sponsor) will be submitted to the regulatory bodies/local health authorities (in accordance with local regulations) and to the IEC for evaluation. The protocol will also be signed by the principal investigator before submission to the IEC. The study will not start before the IEC gives written approval or a favourable opinion in accordance with ICH E6-GCP and all applicable regulatory bodies/local health authorities give approval or a favourable opinion as required.

No changes from the final approved (authorised) protocol will be initiated without the IEC's prior written approval or favourable opinion of a written amendment, except when necessary to eliminate immediate hazards to the subjects or when the change involves only logistics or administration. The Sponsor will authorise and the principal investigator(s) will sign the protocol amendment prior to submission to the IEC. Protocol amendments should be submitted to the IEC without delay.

GE Confidential Page 33 of 43

9.10.1 Overall Responsibilities of Investigators

The investigators are responsible for conducting the study in full accordance with the Protocol and the Declaration of Helsinki, the *Good Clinical Practice: Consolidated Guideline*, approved by the ICH, and any applicable national and local laws and regulations. Information regarding any investigational centres participating in this study that cannot comply with these standards will be documented.

9.10.2 Subject Informed Consent

When informed consent is required by the local IEC, written and oral information about the study in a language understandable by the subject will be given to all subjects. Each subject's willingness to participate in the study will be documented in a signed and dated informed consent form before any procedures or assessments are done and after the aims, methods, anticipated benefits, potential hazards, and insurance arrangements in force are explained. It will also be explained to the subjects that they are free to refuse entry into the study and free to withdraw from the study at any time without prejudice to future treatment. The informed consent process will be documented in the subject's medical record and the investigator will sign, date and time the informed consent form after the subject has signed, dated, and recorded the time. The investigators will keep the original consent forms and copies will be given to the subjects.

9.10.3 Protocol Deviations

Any deviation from the protocol when no approved amendment exists must be documented as a protocol deviation and reported according to local requirements. If appropriate, corrective and preventative action must be implemented to avoid repetition. Protocol deviations and any potential impact on the study results will be discussed during the reporting of the study.

Waivers or protocol exceptions will not be granted prospectively by the Sponsor under any circumstances.

GE Confidential Page 34 of 43

10 PROTECTION OF HUMAN SUBJECTS

The study protocol will be reviewed by an IEC at each imaging site. Each participating subject and clinical reader must provide informed consent prior to participation.

Subject and clinical reader confidentiality will be maintained in accordance with local requirement. The legislation applicable to this study on data protection with regard to the processing of personal data and on the free movement of such data will be followed.

11 MANAGEMENT AND REPORTING OF ADVERSE EVENTS/ADVERSE REACTIONS

11.1 Safety Assessments

The imaging agent VIZAMYLTM is approved and non-investigational in this study. It will be ordered and used in the course of everyday clinical practice. For the purposes of this study it is not considered to be an intervention. The collection of safety data is therefore aimed at post-approval supplementation of the safety profile described in the VIZAMYLTM Summary of Product Characteristics.

The investigator(s) and the Sponsor will review the data on treatment-emergent events (AEs and SAEs).

The Sponsor will periodically monitor the data generated during study conduct and consider any implications for the risk-benefit balance of VIZAMYL in Global Pharmacovigilance safety signal management.

11.1.1 Treatment-Emergent Adverse Events

Study personnel must remain vigilant for the occurrence of AEs, particularly those that may be life-threatening. Personnel who are trained in the acute management of anaphylaxis and other emergencies and who have access to appropriate clinical supplies must be immediately available for 30 minutes after dosing. Treatment of SAEs should be primarily supportive of vital functions.

AE Definition: An AE is defined as any untoward medical occurrence in a patient or clinical investigation subject administered a pharmaceutical product and which does not necessarily have a causal relationship with this treatment. An AE can therefore be any unfavourable and unintended sign (including an abnormal laboratory finding), symptom, or disease temporally associated with the use of a study drug, whether or not considered related to that product. Only symptoms/signs that begin or worsen in severity and/or frequency after study drug administration/use will be recorded as AEs in the eCRF.

The subjects will be closely observed and questioned for any kind of AE during the study procedures and at follow-up appointments throughout the study period with non-leading questioning (e.g., "How do you feel?"). The subjects will be instructed to immediately report any symptoms and signs to the study staff (i.e., between formal observations).

Both the investigator(s) and Sponsor will perform a causality assessment on any AE, to assess whether or not there is a reasonable possibility (evidence to suggest) that the study drug caused the event.

Expectedness of an AE/reaction will be assessed against the approved VIZAMYLTM Summary of Product Characteristics.

Adverse Reaction: An AE that is caused by the study drug.

GE Confidential Page 36 of 43

Suspected Adverse Event: A reasonable possibility exists for causality between the study drug and the AE.

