Sensitivity, specificity, PPV, and NPV will also be calculated:

$$\text{Sensitivity} = \text{nTP} / (\text{nTP} + \text{nFN})$$

$$\text{Specificity} = \text{nTN} / (\text{nTN} + \text{nFP})$$

$$\text{PPV} = \text{nTP} / (\text{nTP} + \text{nFP})$$

$$\text{NPV} = \text{nTN} / (\text{nTN} + \text{nFN})$$

Treatment-emergent adverse events (AEs) with onset or worsening between the start of VIZAMYL™ injection and subject discharge from the imaging suite will be recorded on an adverse event (AE) eCRF, along with the centre's assessment of relationship to VIZAMYL™, severity, seriousness, timing, need for treatment, and outcome.

Study procedures for prospective data collection are summarised in the Study Schedule of Events for Prospective Data Collection ([Table 3-1](#)). For collection of existing data, the activities in the “Subject Enrolment” and “Imaging Visit” columns in [Table 3-1](#) will have occurred in the past and may be obtained from the medical record, including whether or not the patient meets the inclusion and exclusion criteria.

Table 3-1 Study Schedule of Events for Prospective Data Collection

Procedures	Subject Enrolment	Imaging Visit	Post-Imaging	Responsible
Selection of imaging sites				Sponsor
Informed consent obtained from subject (if IEC requires)	X			Centre
Subject inclusion/exclusion criteria assessed	X			Centre
Subject demographic information recorded	X			Centre
VIZAMYL™ administration and PET imaging; AE monitoring from start of injection until discharge from imaging centre		X		Centre
Completion of electronic case report form			X	
De-identification of subject's images			X	Centre
Transmittal of subject's images to Sponsor image core lab			X	Centre
Preparation of images for expert readers			X	Sponsor

The image evaluation by expert readers will be prospective; these activities are summarised in [Table 3-2](#).

Table 3-2 Study Schedule of Events for Image Evaluation by Expert Readers

Procedures	Expert Selection	Expert Image Evaluation	Responsible
Identification of expert reader candidates	X		Sponsor
Informed consent obtained from expert reader candidates	X		Sponsor
Expert reader candidate inclusion/exclusion criteria assessed	X		Sponsor
Selection of 5 expert readers	X		Sponsor
Expert reader demographic information recorded	X		Sponsor
Independent review of images		X	Readers

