8.7 Safety analyses

8.7.1 Adverse events

All AEs will be classified by primary system organ class (SOC) and preferred term (PT) according to the Medical Dictionary for Regulatory Activities (MedDRA).

A treatment-emergent AE (TEAE) is defined as an AE that begins or worsens in severity after at least one dose of study treatment has been administered.

AE summary tables will be presented for TEAEs only and will include the following:

- All TEAEs
- Subject with at least one TEAE
- Related TEAEs
- TEAEs by maximum severity
- Serious TEAEs

An overall summary for the above categories will be presented. All TEAEs categories presented above will also be summarised by SOC and PT using frequency counts and percentages (i.e., number and percentage of subjects with an event). The safety population will be used for these summaries.

If a subject has the same AE, based on PT, reported multiple times in the treatment period, the subject will only be counted once at the PT level in AE frequency tables.

If a subject has multiple AEs within the same SOC in the treatment period, the subject will only be counted once at the SOC level in the AE frequency tables.

When reporting AEs by severity, in addition to providing a summary table based on the event selection criteria detailed above, a summary table will also be provided based on the most intense event during the treatment period, independent of relationship to study treatment.

In the summaries by SOC and PT, AEs will be sorted by decreasing frequency within each SOC and PT within each SOC.

Individual listings will be provided for AEs.

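### The SAP's definition of a treatment-emergent AE leaves out worsening in frequency, which the protocol records, so such AEs may be missing from the summary tables

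*Protocol*

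**What the plan says.** Protocol 11.1.1, under its heading on treatment-emergent adverse events, gives the condition for entering an AE: "Only symptoms/signs that begin or worsen in severity and/or frequency after study drug administration/use will be recorded as AEs in the eCRF". A rise in frequency is therefore enough on its own.

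Protocol 9.1.1 and SAP 3.1 describe treatment-emergent AEs more briefly. In the SAP they are events "with onset or worsening between the start of VIZAMYL™ injection and subject discharge from the imaging suite". Neither text says which kind of worsening is meant.

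SAP 8.7.1 gives the definition used for analysis. A treatment-emergent AE (TEAE) is "an AE that begins or worsens in severity after at least one dose of study treatment has been administered". The same section states: "AE summary tables will be presented for TEAEs only". It adds: "Individual listings will be provided for AEs", with no restriction to TEAEs.

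Protocol 9.7 plans summaries of treatment-emergent AEs by system organ class, preferred term, relationship and severity. It does not limit worsening to severity. SAP section 9 reports no change from the analysis planned in the protocol.

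**The concern.** The protocol has two routes by which a pre-existing sign can worsen into a recordable AE, and the SAP definition keeps one of them. Since the tables admit only TEAEs, an event collected through the other route may not be counted, although the site recorded it correctly. The issue is the kind of worsening that qualifies, not the length of the collection window.

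The tables supply the reported safety percentages: subjects with at least one TEAE, related TEAEs, and the rows by system organ class and preferred term. Protocol 11.1 says that safety data are collected to supplement the profile in the Summary of Product Characteristics. A definition narrower than the collection rule can only lower those counts relative to the protocol. The SAP gives no reason for the narrowing and does not acknowledge it.

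**Working it through.** No figure in the plan can be reproduced here. The check is to apply the two rules to each way in which an AE can be recorded.

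| Post-dose change | Recorded under protocol 11.1.1? | TEAE under SAP 8.7.1, read literally? | In summary tables? | In listings? |
|---|---|---|---|---|
| New onset | Yes | Yes | Yes | Yes |
| Pre-existing sign, worse in severity | Yes | Yes | Yes | Yes |
| Pre-existing sign, more frequent, same severity | Yes | No | No | Yes |

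Only the third row differs between the documents. Its result depends on how the event is entered. If the site enters the increase as a new AE with a post-dose onset date, it begins after dosing and moves to the first row. If the onset is that of the underlying sign, it stays in the third row. Neither document says which applies.

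**Size per subject.** The input is the planned minimum of 200 subjects (protocol 9.5, SAP section 5). The safety population is everyone enrolled and dosed, and subjects whose scans cannot be interpreted or transferred stay in it, so its size N should be at least 200 if the target is met.

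- Change in the proportion with at least one TEAE, per omitted subject with no other TEAE: 1/N = 1/200 = 0.005, or 0.5 percentage points. A larger N makes it smaller.
- If the omitted subject has another TEAE, that proportion does not change. SAP 8.7.1 counts a subject once per preferred term and once per system organ class, so only the rows to which the omitted event alone would have contributed fall, by the same 1/N.

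**Number of such subjects.** The documents give no AE rates, so this cannot be estimated. The collection rules suggest that it is small. There is a single diagnostic administration. Under protocol 11.1.4, AEs of any cause are recorded from injection to discharge, and later ones only if a causal relationship is a reasonable possibility. For existing data, the chart review covers injection to discharge only.

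**The case against.** The strongest reply is that nothing need be lost. Protocol 11.1.1 makes a pre-existing sign an AE only once it changes after dosing, so the recorded AE is arguably the change itself, which begins after dosing and meets the first limb of the SAP definition. This is a possible reading, and it is why omission cannot be stated as certain. But the SAP does not adopt it, and the separate limb for worsening in severity suggests that worsening is handled apart from onset. Leaving the choice to data entry or programming is the ambiguity to remove.

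Second, the protocol sentence is a recording rule rather than a definition of treatment emergence, and protocol 9.7 leaves analysis details to the SAP. That weakens any criticism of SAP section 9. It does not explain why SAP 8.7.1 is narrower than SAP 3.1.

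Third, protocol 11.1.4 grades intensity by tolerability and interference with activity, so a marked rise in frequency could itself raise the grade and satisfy the severity limb. This stands, and it shrinks the affected group to increases in frequency within one grade.

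Fourth, the events remain in the listings. That is correct, so they are not lost from the report. A listing does not, however, contribute to the percentages.

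**Conclusion.** The mismatch is real and minor. On a literal reading of SAP 8.7.1, an AE recorded solely for increased frequency may be left out of the TEAE tables. The size is at most 0.5 percentage points per omitted subject with N of at least 200, and the number of such subjects is unknown and probably very small or zero. The result rests on the SAP definition being programmed as written and on the worsening not being entered as a new onset.

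A reader might infer that such AEs will certainly be absent from every table, or that the reported AE rate is biased downward as a matter of fact. The documents support neither. The onset route is open, and nothing shows that any frequency-only event will occur. A reader might also imagine all of the study's AEs disappearing from the tables. That would require every one of them to be a frequency-only worsening, an extreme for which the documents give no basis.

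Diagnostic accuracy, sensitivity, specificity, the predictive values and the sample size reasoning are untouched.

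**What to change.** In SAP 8.7.1, change the worsening limb of the TEAE definition from severity alone to severity and/or frequency. The tables then cover every AE recorded under protocol 11.1.1, and the definition agrees with the unrestricted wording in SAP 3.1 and protocol 9.1.1. If the narrower definition is intended, declare and justify it in SAP section 9 instead.

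The cost is a few words in the SAP and the matching TEAE flag in the AE dataset. No new data are needed. The reported TEAE count may be slightly higher.

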11.1.2 Serious Adverse Events

An SAE is defined as any AE that:

- Results in death.
- Is life-threatening.
- Requires in-patient hospitalization or prolongation of existing hospitalization.
- Results in persistent or significant disability or incapacity.
- Is a congenital anomaly or birth defect.
- Is another important medical event.*

*Other important medical events are those that may not result in death, be life threatening, or require hospitalization, but may be considered an SAE when, based upon appropriate medical judgment, they may jeopardise the subject and may require medical intervention to prevent one of the outcomes listed above.

11.1.3 Other Significant Adverse Events

Clinical laboratory abnormalities that qualify as AEs (other than those meeting the definition for serious) and any events that lead to an intervention (including premature discontinuation of study drug, dose reduction or significant additional concomitant therapy), other than those reported as SAEs, will be reported and evaluated as other significant AEs.

11.1.4 Adverse Event and Serious Adverse Event Reporting

All AEs should be recorded using acceptable diagnoses, if possible. If an AE has already been reported it is not necessary to report each individual sign and symptom of that AE as a separate AE. For example, if myocardial infarction is reported as an AE, there is no need to report elevated creatine kinase and abnormal ECG, or other related signs, symptoms, or laboratory values as separate AEs. However, if both occurred in isolation and myocardial infarction was not diagnosed, then each event would be reported as an AE.

The intensity of all AEs will be graded as mild, moderate, or severe using the following definitions:

Mild: Tolerable.

Moderate: Interferes with normal activity.

Severe: Incapacitating (causes inability to perform usual activity or work).

The investigator will be instructed to closely monitor each subject who experiences an AE (whether ascribed to the study drug or not) until the outcome of the AE has been determined.

GE Confidential Page 37 of 43

In addition to the investigator's own description of the AEs, each AE will be encoded by the Sponsor according to a well-recognised dictionary of medical codes.

AEs will be recorded in the eCRF if they occurred as follows:

- From start of injection until discharge from imaging centre, whether or not considered related to the study drug, and
- After discharge from imaging centre, and for which a causal relationship to the study drug is a reasonable possibility.

All serious and non-serious AEs must be followed for a final outcome until the end of the follow-up period. An outcome of "unknown" is not considered to be an acceptable final outcome. An outcome of "not yet resolved" is an acceptable final outcome for non-serious AEs at the end of a subject's participation in a study, and for SAEs at database lock.

Additional information required in cases of hypersensitivity reactions or AEs in patients with renal and/or hepatic impairment.

In accordance with the Risk Management Plan for VIZAMYLTM, hypersensitivity-type adverse reactions (both serious and non-serious) and AEs in patients with renal impairment and/or hepatic impairment (both serious and non-serious) need to be carefully documented. Investigators are requested to fill out the questionnaire (see Annex 1) together with the AE/SAE form.

Study centres are instructed to report all AEs to GE Healthcare Global Pharmacovigilance within 3 days by sending an email to [contact].

Individual case safety reports of valid serious and non-serious adverse drug reactions will be classified as solicited reports. The Sponsor will report adverse drug reactions (i.e., AEs for which a causal relationship is at least a reasonable possibility) to health authorities in accordance with applicable postmarketing reporting requirements and Sponsor SOPs.

Reports of causally unrelated AEs will be summarised as part of any interim safety analysis and in the final study report, where applicable.

Adverse reactions to medicines other than VIZAMYLTM will be handled according to GE Healthcare Global Pharmacovigilance SOPs.

Events which affect the known risk-benefit balance of VIZAMYLTM and/or impact on public health will be notified to competent authorities and the Agency, in accordance with GE Healthcare Global Pharmacovigilance SOPs.

The centre should also notify the Qualified Person Pharmacovigilance (QPPV) of the SAE at one of the contact numbers below. For any protocol or safety-related questions please contact the QPPV:

GE Healthcare [name]

Subjects will be provided with a Clinical Trial Participant card at the time of study drug administration. This card will list contact details for the investigator and for GE Healthcare medical emergency cover services (Clinical Trial Emergency Contact Service [CTECS]). The CTECS provides 24-hour, 7-day-a-week emergency cover service for advice on trial—related medical questions or problems should a medical emergency arise and the investigator is not available.

For collection of existing data, the medical record will be reviewed and any AEs that occurred between the start of injection and discharge from the imaging suite will be recorded in the eCRF and recorded/summarised in the final study report but *not* reported as individual case safety report to competent authorities.

